4.3. Sample Size

Approximately 148 subjects will be enrolled in 4 cohorts (3 cohorts of SKI-O-703 and 1 cohort of placebo). Each cohort will consist of at least 37 subjects.

The study is powered to detect a difference of 0.8 in mean change from baseline to Week 12 in DAS28-hsCRP score between one of the groups treated with SKI-O-703 and the group treated with placebo. At least 37 subjects on a course of SKI-O-703 treatment are required to complete the study to show a change from baseline to Week 12 of 0.80 and higher as statistically significant with a power of 0.80 at the significance level of 0.05, using a 1-way analysis of variance and assuming a standard deviation of 1.25, compared with in the placebo group. Sample size determinations were based on the 4-component DAS28 and are likely to be similar with the 3-component DAS28 with fewer variables.

Given the 1:1:1:1 ratio of SKI-O-703 100 mg BID, 200 mg BID, 400 mg BID to placebo allocation, at least 37 subjects in each treatment group are required to complete the study, therefore at least 148 subjects need to be enrolled and randomized in the study. Assuming a drop-out of rate of 10%, up to 20 additional subjects may be enrolled to achieve the target number of subjects required to complete the study.

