7.3.2. Treatment Compliance

Treatment compliance (%) will be calculated for each subject as 100 times total dose divided by the intended total dose that should be taken over the treatment period. The intended total dose is calculated as 8 times the treatment duration. Compliance will be summarized using descriptive statistics by treatment group. The acceptable range for compliance is defined as between 80% - 120%. The number and percentage of subjects will be summarized by category $< 80\%$, $\geq 80\%$ to $\leq 120\%$, and $> 120\%$.

A subject data listing of study drug accountability will be provided, with the capsules dispensed, capsules returned, capsules taken, intended total dose and treatment compliance presented.

8. Efficacy Analysis

The primary analyses of all efficacy endpoints will be based on the ITT set, and then repeated using the PP set. The analyses of primary endpoint and secondary efficacy endpoints ACR20, ACR50 and ACR70 will also be provided based on the mITT set.

Each efficacy endpoint will be descriptively summarized by treatment group over time. In the summary for a post-baseline time point, subjects who have both values at baseline and at the time point will be included. Listings of all the efficacy endpoints will be provided by subjects.

Statistical comparisons will be performed between each of active treatment groups and the placebo group. All the statistical tests will be 2-sided and performed at a significance level of 0.05, leading to 95% CIs (2-sided). There will be no adjustment for multiplicity.

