8.2.3. Sensitivity Analysis: Using MI Under MAR Framework

Repeat the primary analysis on the ITT set and before calculating the DAS28-hsCRP, the missing value of each individual component (TJC28, SJC28 and hsCRP) will be imputed by multiple imputation (MI) method for all treatment groups as described below, under the missing at random (MAR) framework.

The SAS procedure MI will be used to impute the missing value for each individual component at the scheduled post-baseline analysis visits (up to Week 12) to create 25 complete data sets. The missing data patterns will be checked by treatment and at scheduled visits. If there are non-monotone missing patterns, two separate imputation procedures as described below will be used to complete the imputation process; otherwise, skip the first step. For components SJC28 and TJC28, the imputed values will be rounded to integers. The range of imputed value should be from minimum value 0 to maximum value 28 for SJC28 and TJC28. The minimum value for hsCRP should be 0.

In the first step, the Markov Chain Monte Carlo (MCMC) method will be used to impute missing values by treatment to create 25 imputed data sets with monotone missing patterns. The seed will be set to 7032101 and a single chain will be used to procedure imputations.

In the second step, the monotone regression method will be used to impute the remaining missing values for the 25 data sets with monotone missing patterns. The MONOTONE REG statement will be used with the seed 2101703. The missing values at each visit will be imputed based on treatment, stratification factors (prior anti-TNF α biologic agents use, number of

previous csDMARDs treatments, geographic region) and values at baseline and previous visits. (If the imputation cannot be implemented due to lack of sufficient subjects in a specific stratum, remove the factor from the imputation model.)

After the completion of two steps imputations, calculate the DAS28-hsCRP based on the values of individual components in the 25 complete datasets and the same statistical analysis method described in the primary analysis will be conducted for each of the 25 completed datasets. The SAS procedure MIANALYZE will be used to combine the results for the statistical inferences.

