8.2.4. Sensitivity Analysis: Excluding Local hsCRP Values

The primary analysis will also be repeated based on the ITT set using the hsCRP value analyzed from central laboratory. The hsCRP results from local laboratory (if any) will be considered as missing. Then all missing data up to Week 12 will be imputed by MI method under:

- MAR framework.
Under this framework, the same MI method will be applied as outlined above.
- Missing not at random (MNAR) framework.

Two imputation steps will be performed. First step is to create 25 datasets with monotone missing patterns which is the same as described above under MAR framework. The second step is control-based pattern imputation using monotone regression method with seed 2010703, in which the missing data in all active treatment groups and placebo group will be imputed based on placebo group.

The same statistical analysis method described in the primary analysis will be conducted for each of the 25 completed datasets, and the SAS procedure MIANALYZE will be used to combine the results for the statistical inferences.

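### Multiple imputation of TJC28, SJC28 and hsCRP on the raw scale does not match a score built from square roots and a logarithm, and slightly distorts the MI sensitivity analyses.

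*SAP*

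**What the plan says.** SAP 8.1.1 defines the score as DAS28-hsCRP(3) = [0.56 sqrt(TJC28) + 0.28 sqrt(SJC28) + 0.36 ln(hsCRP+1)] x 1.10 + 1.15.

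SAP 8.2.3 imputes the three components before the score is calculated. MCMC by treatment makes the missing pattern monotone; MONOTONE REG fills in the rest; 25 data sets result. On the imputed values it says "For components SJC28 and TJC28, the imputed values will be rounded to integers", limits the counts to 0-28, and adds "The minimum value for hsCRP should be 0". It names no transformation and does not say what happens to a draw outside the range.

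SAP 8.2.4 sets local-laboratory hsCRP results to missing and imputes again. For its MAR branch, "Under this framework, the same MI method will be applied as outlined above". Its MNAR branch takes over the first step and specifies its own control-based monotone regression for the second.

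The primary analysis (SAP 8.2.1) is an ANCOVA on observed cases without imputation.

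**The concern.** MCMC and monotone regression, as named, are linear models with normal errors. hsCRP is usually right-skewed, and joint counts become so as subjects improve. A normal model fitted to such data puts part of its mass below zero, and the bound has to remove it. Redrawing moves that mass upward; clipping piles it up at exactly zero. The logarithm and the square root are steepest near zero, so what happens there feeds directly into the score.

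Low values are within the range the plan itself considers. SAP 8.4 uses cut-offs of 3.2 and 2.6. With hsCRP 3 mg/L and equal tender and swollen counts n, the formula gives 0.84 sqrt(n) = (3.2 - 1.15)/1.10 - 0.36 ln 4 = 1.36, so n is about 2.6. For 2.6 it gives 0.82, so n is about 1.0.

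The primary analysis drops subjects without a Week 12 score, so the MI analyses are its main model-based check on missing data. An artefact of the imputation scale could be mistaken for sensitivity to the missing-data assumption.

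**Working it through.** **1. Yardstick from the plan.** The documents give no figure for the imputation, so the planned precision serves as the scale. The SAP states: "The study is powered to detect a difference of 0.8 in mean change from baseline to Week 12 in DAS28-hsCRP score", "with a power of 0.80 at the significance level of 0.05", "using a 1-way analysis of variance and assuming a standard deviation of 1.25". The normal formula gives n = 2 x (1.25/0.8)^2 x (1.960 + 0.842)^2 = 38.3, so 39 per arm against the stated 37; power at 37 is 78.6%. The stated size is reproduced closely. The planned standard error of a difference is 1.25 x sqrt(2/37) = 0.29.

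**2. hsCRP component.** Assumed: lognormal hsCRP at Week 12, median 3-12 mg/L, log-SD 0.6-1.2, replaced by a normal with the same mean and SD. The weight in the score is 0.36 x 1.10 = 0.396.

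Example with median 8 and log-SD 1.0:
- Mean = 8 x exp(0.5) = 13.2; SD = 13.2 x sqrt(e - 1), about 17.3 allowing for rounding.
- Share of draws below zero = Phi(-13.2/17.3) = Phi(-0.76), about 22%.
- Redraw: the mean of ln(hsCRP+1) is 0.53 too high, and 0.396 x 0.53 = +0.21 score units.
- Clip: it is 0.09 too low, and 0.396 x (-0.09) = -0.035.

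Over the whole range, redrawing gives +0.03 to +0.36 and clipping -0.06 to +0.04. With clipping, the SD of the imputed component is inflated by about 34-64% (medians 3-10 mg/L).

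**3. Joint counts.** Assumed: beta-binomial counts out of 28, mean 2-14, with the same replacement. For TJC28, redrawing gives 0.00 to +0.67 and clipping -0.01 to +0.31; SJC28 has half of that (0.28 against 0.56). The bias is near zero at a mean of about 14 and large at 2-4.

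**4. Whole trial.** Steps 2 and 3 ignore predictors. In the plan, each draw is conditional on baseline and earlier visits, which narrows the residual spread and sends fewer draws out of range. A simulation allowed for this: 4 x 41 subjects, five visits, monotone MAR dropout depending on the previous score, sequential Bayesian regression imputation, 10 imputations, 250 replicates. Entries are the mean error of the imputed Week 12 score, then the active-placebo difference.

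| Scenario | Full data | Raw, redraw | Raw, clip | sqrt / ln scale |
|---|---|---|---|---|
| 10% dropout | -0.744 | +0.154; -0.735 | -0.030; -0.742 | -0.001; -0.742 |
| 20% dropout | -0.767 | +0.162; -0.742 | -0.025; -0.762 | +0.008; -0.762 |
| 10%, heavier hsCRP tail | -0.748 | +0.297; -0.736 | -0.003; -0.742 | +0.004; -0.745 |

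Under redrawing the difference shrinks by 0.009, 0.025 and 0.012. That is 6-15% of the simulated standard error (0.163-0.175), or 3-9% of the planned 0.29. The Monte Carlo standard error of each mean difference is about 0.009, but all columns share the same simulated trials. Under redrawing 58-63% of imputed scores exceeded the true value, so 37-42% fell below it.

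Under clipping, the average standard error within imputed data sets was 0.166, 0.169 and 0.177, against 0.163, 0.164 and 0.173 on the transformed scales, so 2-3% larger.

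**The case against.** The strongest reply is that this hardly matters. The primary analysis does not use the imputation, and the LOCF analysis (SAP 8.2.2) is free of this model. The shift is largely shared by the arms, and the treatment difference barely moves. All of that stands, and it sets the weight of the point.

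The SAP also does not say that draws are redrawn. With clipping, the mean error is about zero. That stands too, but clipping does not make the method sound: it exchanges a mean bias for a distorted spread in the hsCRP component.

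Nor do the documents say that counts pile up near zero. Entry requires at least 5 tender and 5 swollen joints (Protocol 4.1.1), and no Week 12 distribution is given. The joint-count part is therefore uncertain and could be near nil.

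It might be said that a transformation was intended and left out of the text. Rounding to whole joints and an upper limit of 28 make sense only on the raw scale, so the text is best read as raw-scale imputation.

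A reader might infer that rounding adds to the upward bias. It does not: in a check it lowered it slightly (0.178 to 0.163 in one case). Observed counts are themselves whole numbers unless prorated for missing or non-evaluable joints (SAP 8.1.3).

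**Conclusion.** The imputation in SAP 8.2.3 works on a different scale from the endpoint. The same holds in 8.2.4 under MAR and in the first MNAR step. Under redrawing, imputed Week 12 scores are too high on average, by about 0.15-0.30 units. Under clipping, the mean is nearly right, but the imputed hsCRP component is spread about 34-64% too widely. At 10-20% missing the treatment difference moves about 0.01-0.025 toward the null under redrawing, in sensitivity analyses only.

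A reader might infer that every imputed score is pushed upward, that the components add up to roughly half a unit per score, or that the treatment difference shifts by 0.05 or more. The documents do not support this. The bias is an average and depends on an unstated rule. The simulation that conditions on earlier visits gives smaller figures, and the plan assumes 10% dropout without a difference between arms. In 8.2.4, a subject who lacks only hsCRP keeps the observed joint counts, so only the hsCRP part applies.

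The sizes rest on assumed distributions, visit correlations and dropout. The simulation used monotone dropout and 10 imputations rather than 25, so it did not exercise the MCMC step. This is a free improvement, not a threat to the primary result.

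**What to change.** In SAP 8.2.3, derive sqrt(TJC28), sqrt(SJC28) and ln(hsCRP+1) at every visit and use them in both the MCMC and the monotone-regression step. Set the bounds on those scales (0 to sqrt(28) = 5.29 for the counts, minimum 0 for the log term) and state whether out-of-range draws are redrawn or set to the bound. Delete the rounding, which is unnecessary on those scales. Then compute DAS28-hsCRP(3) from the imputed values. In the simulation this left a mean error of -0.001 to +0.008.

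Carry the same scales into 8.2.4, including the MNAR second step, which also names monotone regression without a scale. Do not impute the DAS28 score directly where some components are observed: in 8.2.4 that would discard the joint counts of subjects who lack only a central hsCRP value.

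The cost is a few lines of text and code before the SAP is signed, which its Introduction places ahead of the final database lock. No subjects, visits or data are added.

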8.2.4. Sensitivity Analysis: Excluding Local hsCRP Values

The primary analysis will also be repeated based on the ITT set using the hsCRP value analyzed from central laboratory. The hsCRP results from local laboratory (if any) will be considered as missing. Then all missing data up to Week 12 will be imputed by MI method under:

- MAR framework.
Under this framework, the same MI method will be applied as outlined above.
- Missing not at random (MNAR) framework.

Two imputation steps will be performed. First step is to create 25 datasets with monotone missing patterns which is the same as described above under MAR framework. The second step is control-based pattern imputation using monotone regression method with seed 2010703, in which the missing data in all active treatment groups and placebo group will be imputed based on placebo group.

The same statistical analysis method described in the primary analysis will be conducted for each of the 25 completed datasets, and the SAS procedure MIANALYZE will be used to combine the results for the statistical inferences.

8.2.5. Sensitivity Analysis: Using 4-component DAS28-hsCRP

Repeat the statistical analysis (described in [Section 8.2.1](#)) on the ITT set using 4-component DAS28-hsCRP as calculated in [Section 8.1.1](#). Only subjects who completed the subject global assessment of disease activity consistently will be included in this sensitivity analysis.

8.3. Secondary Efficacy Endpoints

8.3.1. Primary Analysis

The primary analysis will be conducted on observed cases without any imputation. All the secondary efficacy endpoints will be summarized and analyzed by treatment group at each schedule visit (Week 2, 4, 8, and 12) based on the ITT set and then repeated on the PP set.

The DAS28-related secondary endpoint is based on 3 individual components including TJC28, SJC28 and hsCRP (see calculation in [Section 8.1.1](#)). The analyses on ACR responses (ACR20, ACR50 and ACR70) will be restricted to subjects who completed subject global assessment of disease activity consistently, as well as physician global assessment of disease activity and subject assessment of arthritis pain, using the same approach as the sensitivity analysis on 4-component DAS28-hsCRP to identify the subjects to be included in the analysis. Similar to the

analyses on ACR responses, the analyses on the individual component using VAS will be restricted to subjects who completed the corresponding individual VAS assessment.

Frequency counts and percentages will be provided for ACR responses (ACR20, ACR50, and ACR70) at each schedule visit. The Chi-square tests will be used to compare the ACR response rate between each of active treatment group and placebo group, and among active treatment groups at each schedule visit. The p-values from the Chi-square tests will be presented. In case of few responders where Chi-square test may not be appropriate or accurate, Fisher's exact test will be performed instead. Besides, 95% CI of binomial proportion of ACR response within each treatment group and 95% CI of the difference in proportion of subjects with ACR response for pairwise treatment comparison will be estimated using the Wald method.

The hsCRP will be summarized descriptively by treatment group over schedule visits. No inferential statistics will be provided.

For all other secondary efficacy endpoints, descriptive statistics of baseline, observed value and change from baseline at each schedule visit will be provided by treatment group. Treatment comparisons will be conducted using a mixed model repeated measure (MMRM) analysis, including all the scheduled visits up through Week 12. The model will be fitted with treatment group, visit, treatment by visit interaction and baseline as fixed effects, and visit within subject as a repeated effect, using an unstructured covariance to model the between- and within-subject errors. If the model fails to converge with unstructured covariance matrix, use the heterogeneous Toeplitz covariance structure, followed by the heterogeneous autoregressive covariance, followed by the compound symmetry covariance structure. The inferential statistics from this model, including within-group LS means and the associated SE, treatment differences in LS means and the associated SEs, the 2-sided 95% CIs, the 2-sided p-values for treatment comparisons between each of active treatment group and placebo, and the 2-sided p-values for treatment comparisons among different active treatment groups (high dose vs. low dose) will be provided.

Listings for ACR responses, DAS28-hsCRP assessments, number of tender and swollen joints, subject assessment of pain using VAS, subject and physician global assessment of disease activity and HAQ-DI will be provided.

Plots of LS mean change from baseline in continuous primary and secondary efficacy endpoints by visit will be provided as well. Proportion of subjects with ACR response will be plotted by visit.

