8.4. Other Efficacy Endpoints

Based on the DAS28-hsCRP (based on 3 components including TJC28, SJC28 and hsCRP), we will evaluate if the subject achieves the following disease activity category at each schedule visit:

- DAS28-hsCRP ≤ 3.2
- DAS28-hsCRP < 2.6

The frequency counts and percentages of above DAS28 binary endpoints will be provided by treatment group at each schedule visit based on the ITT set and the PP set. The Chi-square tests will be used to compare the response rate between each of active treatment groups and placebo group, and among different active treatment groups. Besides, 95% CI of binomial proportion of ACR response within each treatment group and 95% CI of the difference in proportion of subjects with ACR response for pairwise treatment comparison will be estimated using the Wald method.

The analyses will also be analyzed based on the mITT set, where NRI method will be used to impute missing value. If at least 1 of the 3 components (TJC28, SJC28 and hsCRP) is non-missing at the given visit and the subject is still enrolled in the study, then use LOCF method to fill in any missing values for the 3 components. Then calculate the DAS28-hsCRP and evaluate the DAS28 binary endpoints as defined above. If all the individual components are missing at the given visit or if prior to the visit the subject is considered discontinued from the treatment, assign the subject as a non-responder.

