8.5. Subgroup Analysis

The focus of subgroup analysis will be limited to the baseline characteristics as listed below and the subgroup analysis will be conducted based on the ITT set for all the secondary efficacy endpoints specified in [Section 3.2.2](#). For VAS-related secondary endpoints (ACR responses and individual VAS assessments), the subgroup analysis will be restricted to subjects who completed the corresponding related VAS assessment consistently, same approach as described in the [Section 8.3.1](#) to identify the subjects to be included in the analyses.

- Number of previous csDMARDs treatments (0–2 csDMARDs, ≥ 3 csDMARDs)
- Previous anti-TNF α biologic agents use (Yes or No)
- Specific geographic region (APAC, EMEA, NA)

For ACR response endpoints, the number and percentage of responder and 95% Wald CIs will be provided by visit for each subgroup. The p-value of treatment comparison will be estimated by Chi-square tests within each subgroup. If all the subjects within a subgroup are responders or non-responders at a visit, only frequency counts and percentages will be provided for that subgroup and visit.

For other efficacy endpoints, the descriptive statistics of baseline, absolute value and change from baseline will be summarized by treatment group, scheduled visit and subgroup. By using the MMRM analysis as described in [Section 8.3.1](#), for each subgroup, the inferential statistics for treatment effect estimation and treatment comparisons will be provided by visit. In addition, subgroup comparison within treatment group will be provided as well by using a MMRM

analysis, which will be fitted with treatment group, subgroup, visit, treatment by visit interaction, treatment by subgroup interaction and baseline as fixed effects, and visit within subject as a repeated effect.

If too few subjects fall in the subgroup, the analysis within the subgroup may not be performed and only descriptive summary will be presented.

9. Safety Analysis

All the Safety analyses will be based on the Safety set.

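### Wald 95% intervals are prescribed for response rates and differences at about 37 per arm or fewer; where rates are low they under-cover, and a score-type interval would cost nothing

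*SAP*

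**What the plan says.** **ACR20, ACR50 and ACR70 (SAP 8.3.1).** At Weeks 2, 4, 8 and 12 the SAP asks for a "95% CI of binomial proportion of ACR response within each treatment group" and for an interval on each pairwise difference: "95% CI of the difference in proportion of subjects with ACR response for pairwise treatment comparison will be estimated using the Wald method". For the test, though not the interval, it provides for sparse tables: "In case of few responders where Chi-square test may not be appropriate or accurate, Fisher's exact test will be performed instead". The analysis uses observed cases and is limited to subjects who completed the three VAS scales consistently. SAP 8.3.2 applies the same methods to the mITT set with non-responder imputation.

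**DAS28-hsCRP ≤3.2 and <2.6 (SAP 8.4).** Intervals for the rates and pairwise differences "will be estimated using the Wald method". The sentence still names ACR response, but it can only sensibly refer to the DAS28 thresholds. There is no Fisher fallback here. The VAS restriction does not apply, because the score has three components.

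**Subgroups (SAP 8.5).** For ACR response, "the number and percentage of responder and 95% Wald CIs will be provided by visit for each subgroup". This section alone deals with degenerate data: "If all the subjects within a subgroup are responders or non-responders at a visit, only frequency counts and percentages will be provided". It also allows a purely descriptive summary where a subgroup has too few subjects.

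**Size (SAP 4.3).** The plan states that "at least 37 subjects in each treatment group are required to complete the study", and that "up to 20 additional subjects may be enrolled to achieve the target number of subjects required to complete the study".

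**The concern.** The Wald interval takes its standard error from the observed proportion. When that proportion is near zero the standard error is too small, and at exactly zero it vanishes. The SAP accepts that the large-sample test can fail with few responders, yet keeps an interval that rests on the same kind of approximation.

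At stake is the precision reported for secondary, other and subgroup endpoints. An interval labelled 95% may cover far less often, an arm with no responders gets an interval of no width, and an interval may exclude zero beside a Fisher p-value well above 0.05.

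**Working it through.** **Planning size.** The 37 reproduces as a four-group one-way ANOVA with one group differing by 0.8 and SD 1.25. The noncentrality is n × 0.48 / 1.5625, where 0.48 = 3 × 0.2² + 0.6². Power is 0.794 at n = 36 and 0.806 at n = 37. This confirms 37 as the working size but says nothing about response rates. The 20 extra subjects would give at most 37 + 20/4 = 42 per arm.

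**Assumed inputs.** The documents state no ACR or DAS28 response rates and no number of consistent VAS completers. The rates below are assumptions, shown over a range.

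**Formulas.** With p̂ = x/n and z = 1.96:
- Wald, one rate: p̂ ± z√[p̂(1−p̂)/n].
- Wald, difference: (p̂₁−p̂₂) ± z√[p̂₁(1−p̂₁)/n + p̂₂(1−p̂₂)/n].
- Wilson: [p̂ + z²/2n ± z√(p̂(1−p̂)/n + z²/4n²)] / (1 + z²/n). Newcombe combines the two Wilson intervals.
- Coverage: the summed binomial probability of every outcome whose interval contains the true value.

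**One rate, by hand.** At n = 37 and p = 0.02, the Wald interval contains 0.02 only for x = 1 to 4. Since P(X=0) = 0.98³⁷ = 0.474, coverage is about 0.526. At p = 0.05 it contains 0.05 for x = 1 to 6, and P(X=0) = 0.95³⁷ = 0.150, so coverage is 0.848.

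| True rate (assumed), n = 37 | Wald | Wilson |
|---|---|---|
| 2% | 0.526 | 0.962 |
| 5% | 0.848 | 0.964 |
| 8% | 0.799 | 0.974 |
| 10% | 0.887 | 0.952 |
| 15% | 0.914 | 0.940 |
| 20% | 0.946 | 0.963 |
| 25% | 0.917 | 0.944 |
| 30% | 0.943 | 0.953 |
| 40% | 0.936 | 0.956 |
| 50% | 0.953 | 0.953 |

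Coverage moves in steps because the data are discrete, so it does not rise smoothly. At n = 42, Wald still gives only 0.570 at 2% and 0.880 at 5%.

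**A small subgroup.** Protocol 3.1 expects about 30% with prior biologic therapy: 0.30 × 37 ≈ 11 per arm, before the VAS restriction. At n = 11 and a rate of 10%, Wald covers for x = 1 to 4 only. P(X=0) = 0.9¹¹ = 0.314, so coverage is 0.683.

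| Two true rates (assumed), n = 37 per arm | Wald | Newcombe | Chance both arms have 0 responders |
|---|---|---|---|
| 5% v 2% | 0.845 | 0.989 | 7% |
| 10% v 2% | 0.881 | 0.981 | 1% |
| 8% v 3% | 0.930 | 0.973 | 1.5% |
| 10% v 5% | 0.940 | 0.964 | 0.3% |
| 20% v 10% | 0.945 | 0.955 | about 0 |
| 2% v 2% | 0.994 | 0.999 | 22% |
| 5% v 5% | 0.961 | 0.988 | 2% |

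Over a grid of pairs with both rates between 1% and 10%, Wald coverage averages 0.914, with a minimum of 0.635. With both rates between 10% and 30% it is never below 0.939.

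**No responders.** For 0/37, Wald gives 0 to 0 and Wilson gives 0 to 9.4%. At a true rate of 5% this outcome has a 15% chance. The Wald interval for a difference has zero width only if each arm is all responders or all non-responders; for 0/37 v 0/37 Newcombe gives −9.4% to +9.4%.

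**Interval against test.** For 4/37 v 0/37 the difference is 10.8%. Wald gives +0.8% to +20.8%, which excludes zero, while Fisher gives p = 0.115. Newcombe gives −0.6% to +24.7%. The uncorrected Chi-square is 74 × (4×37)² / (37×37×4×70) = 4.23, p = 0.040, so the conflict arises only if the Fisher fallback is used. With expected responders of 4 × 37/74 = 2 per arm, this is the sort of table for which that fallback exists.

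**The case against.** Much of the case on the other side stands.

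- **Rates are unknown.** A reader might infer that ACR50, ACR70, early visits and every subgroup cell are bound to be sparse. The documents do not support this: they give no rates. Low rates are plausible for ACR70, ACR50 and early visits, but they remain an assumption.
- **Coverage is often adequate.** A reader might also infer that none of the 95% intervals has 95% coverage. At n = 37 and single rates from 20% to 50%, the shortfall is between nil and about 3 points, so ACR20 may be little affected. Differences between moderate rates cover about 94%, and two equal low rates are over-covered.
- **Zero width is narrower than it looks.** An empty arm collapses that arm's interval, not the difference. Counts and percentages are printed alongside, so 0/n stays visible.
- **Subgroups are partly handled.** The SAP 8.5 rules help, but the all-or-none rule refers to all subjects in a subgroup and does not clearly cover one empty arm. SAP 8.3.1 and 8.4 have no such rule.
- **Consequences are limited.** P-values for these endpoints come from Chi-square or Fisher tests, no decision rule uses the intervals, and the primary endpoint is continuous.

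These points limit the scope. They do not justify keeping Wald where rates are low.

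**Conclusion.** The point holds as a minor one. SAP 8.3.1, 8.4 and 8.5 name an interval that is unreliable when response rates are about 15% or lower at 37 per arm, or when subgroup cells are small. If true rates lie there, single-arm coverage falls to between about 53% and 91% at rates of 2% to 15%. Differences between unequal low rates can fall to about 85%, and lower at the extreme of the grid. If rates are 20% or more, little changes.

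The inconsistency within 8.3.1, where the test changes for sparse data and the interval does not, is in the text and needs no assumed rate. The effect is on the reported precision of secondary, other and subgroup endpoints. The primary ANCOVA of DAS28-hsCRP is unaffected.

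**What to change.** In SAP 8.3.1, 8.4 and 8.5, replace Wald with Wilson score intervals for single proportions. In 8.3.1 and 8.4, name either Newcombe or Miettinen-Nurminen intervals for differences. While editing 8.4, let the sentence name the DAS28 endpoints.

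The choice between the two should be made with open eyes. Neither guarantees agreement with Fisher's test. At a difference of zero the Miettinen-Nurminen statistic is the Chi-square times (N−1)/N: for 4/37 v 0/37 that is 4.23 × 73/74 = 4.17, above 3.84, so the interval would still exclude zero. Newcombe includes zero there, but for 5/37 v 0/37 it starts at +1.4% while Fisher gives p = 0.054. The gain is in coverage and in non-degenerate limits. Newcombe is somewhat conservative at very low rates.

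The cost is a short edit in three sections and a change of option in the SAS code. No subjects, visits or data are added, and the SAP is to be finalized before database lock. This is a free improvement of minor severity.
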